1.1 Title

Trial of thiamine supplementation in Cambodia

Note that this study was funded using the title: ‘Improving estimates of the global burden of thiamine deficiency disorders (TDDs) and approaches to their control - Objective 3: Trial of thiamine supplementation in Cambodia.’

1.2 Objectives

1. To conduct a dose response supplementation trial among lactating Cambodian women to determine the lowest dose of thiamine that yields the maximum increase in human milk thiamine.
2. To assess rural Cambodian households’ usual salt intake using a household salt disappearance study.
3. To assess cognitive development of infants aged 2 weeks – 12 months to mothers consuming varying thiamine doses using a small battery of cognitive assessments.

1.3 Design

Double-blind, four-parallel arm, placebo-controlled randomized trial.

1.4 Outcomes and Analysis Objectives

The primary outcome of this study is human milk total thiamine concentration at 24 weeks postpartum. The primary objective of this study is to estimate the dose on the dose response curve where additional maternal intake of thiamine (oral dose) no longer meaningfully increases human milk total thiamine concentration at 24 weeks postpartum. A full list of outcomes and analysis objectives can be found in Section 4.

1.5 Study Duration

This is a two-year study, to be completed between 2018 and 2020. The intervention is 22 weeks, from 2 weeks through 24 weeks postnatal, with an additional follow-up at 12 months.

1.6 Interventions

Participants will be randomized to one of four treatment arms, and will be asked to consume one oral capsule daily. Treatment arms are:

- negative control group (placebo; 0 mg thiamine)
- EAR group (1.2 mg thiamine as thiamine hydrochloride)
- double EAR group (2.4 mg thiamine as thiamine hydrochloride)
- positive control group (10 mg thiamine as thiamine hydrochloride)

1.7 Sample size

320 women and their newborn infants.

1.8 Population

Participants must meet the following criteria:

- mothers of a newborn
- aged 18-45 years
- most recent pregnancy was normal (i.e. no known chronic conditions, preeclampsia, gestational diabetes etc.), and the singleton infant was born without complications (e.g. low birth weight (<2.5 kg), tongue tie, cleft palate)
- intends to exclusively breastfeed for six months
- resides in Kampong Thom province, Cambodia, and is not planning to move in the next six months
- is not currently taking, and hasn't taken any thiamine-containing supplements over the previous 4 months
- is not currently participating in any nutrition programs beyond normal care
- is willing to consume one capsule daily from 2 weeks through 24 weeks postpartum
- is willing for her entire household consume only salt provided by the study team
- is willing for the following biological samples to be collected: a maternal venous blood sample and human milk sample at 2 weeks postpartum, a human milk sample at 4 and 12 weeks postpartum, and maternal and infant blood samples and a human milk sample at 24 weeks postpartum.

2. Investigators, Scientific Advisory Board, and Study Locations

2.5 Study Management

The Principal Investigator and Co-Investigators will oversee the coordination of the study; they will meet bi-monthly, or more often if required. Helen Keller International, Cambodia will be the primary implementer of the study, overseeing day-to-day operations, including recruitment, consent, data and biological sample collection, and data management. The Scientific Advisory Board will meet with the investigators annually.

2.6 Serious Adverse Events Committee / Data Safety Monitoring Board

There is no necessity for a Serious Adverse Events Committee or a Data Safety Monitoring Board (DSMB) in the current study because of the absence of potential adverse effects. There is no tolerable upper intake level (UL) for thiamine because there has never been an adverse event reported from high thiamine intake (1,2), even though over-the-counter supplements in Canada and the United States commonly contain 50 mg of thiamine or more. Hence, we are confident that there is a very low risk of serious adverse events in this study related to the intervention.

However, we do expect some infant deaths in our cohort due to other causes. As per the 2014 Cambodian Demographic and Health Survey (CDHS), the rate of neonatal (birth to one month) and infant (birth to one year) mortality was 29 and 11 deaths per 1,000 live births, respectively (3). The majority of neonatal deaths occur in the first 6 days postnatal: in the 4 years preceding the 2014 CDHS data collection, 82% of neonatal deaths occurred in the first 6 days after birth (3). Since this study starts at 2 weeks postnatally, we would expect the mortality rate in our study to lie between 1.67 (neonatal mortality > 6 days postnatal for Kampong Thom = $0.029 \times 0.18 \times 320$) and 3.68 (infant mortality in Kampong Thom = 0.011×320) infant deaths.

2.7 Funding

This study is funded through the Bill & Melinda Gates Foundation and the Sackler Institute for Nutrition Science, New York Academy of Sciences (Opportunity ID OPP1176128) as 'Objective 3: Trial of thiamine supplementation in Cambodia', as part of the larger program grant entitled 'Improving estimates of the global burden of thiamine deficiency disorders (TDDs) and approaches to their control'. The cognitive follow-up assessment at 12 months postnatal is funded by the New York Academy of Sciences.

3. Introduction, Background, and Rationale

3.1 Thiamine, and thiamine deficiency

Thiamine (vitamin B₁) is an essential water-soluble micronutrient required for energy metabolism (4). Thiamine deficiency remains an under-studied public health issue, recently being called the forgotten disease of Asia (5). There is evidence of suboptimal thiamine intake or status throughout Southeast

Asia, notably in Cambodia (6–11), Laos (5,12–14), and among Karen refugees during their early arrival in the Mae La Camp on the Thai-Myanmar border (15,16).

Infantile beriberi, a disease caused by thiamine deficiency, presents during the exclusive breastfeeding period and without treatment can result in death within hours of clinical presentation (15). The dietary staple of Cambodia is B-vitamin poor, white, polished rice; it makes up upwards of 60% of daily energy intake (17). Women with poor dietary thiamine intake produce milk low in thiamine, putting their exclusively breastfed infants at a high risk of developing infantile beriberi (18). We recently demonstrated that maternal consumption of a thiamine-fortified fish sauce significantly increased maternal, human milk, and infant thiamine status (10).

There is also a growing body of evidence suggesting thiamine deficiency not severe enough to cause clinical symptoms has a negative effect on cognitive development and functioning (19–22), though the precise pathways and mechanisms linking these two factors remain poorly understood. Important questions remain about the timing of deficiency, levels of deficiency, and the ability of prophylactic interventions to prevent or therapeutic interventions to remediate the effects of suboptimal thiamine status on cognitive outcomes in humans (23).

3.2 Dietary thiamine requirements

The Institute of Medicine's Dietary Reference Intakes (DRI) can be used to assess dietary thiamine adequacy (24). Thiamine has an estimated average requirement (EAR), the median requirement for a given lifestage group, and a statistically derived recommended dietary allowance (RDA), an estimate of the daily average dietary intake that meets the nutrient needs of 97.5% of healthy members of the group (24). There is no UL for thiamine because there have been no reports of adverse effects of excess thiamine intake (1,2,25). Lactating women secrete an estimated 0.16 mg thiamine per day into human milk, and additional thiamine is required by the mother herself to meet increased energy needs for milk production (1). For lactating women, the EAR and RDA are 1.2 and 1.4 mg/day, respectively (1).

For infants, an adequate intake (AI) was derived due to insufficient evidence to set an EAR and, in turn, a RDA (1). The thiamine concentrations of milk from healthy, well-nourished mothers are extrapolated, assuming a daily milk intake of 780 mL (1). The thiamine AI for infants aged 0-6 months is 0.2 mg/day, however, the evidence base used for setting this AI is poor due to the small sample size and the outdated analytical techniques to assess human milk thiamine concentrations (26).

3.3 Biomarkers of thiamine status

Two biomarkers are used to assess thiamine status. Thiamine diphosphate (ThDP) is the biologically active form of the vitamin (4), and concentrations can be assessed in whole blood or erythrocytes using high performance liquid chromatography with a fluorescence detector (27). Unfortunately there is currently no consensus on the most appropriate ThDP cut-offs for thiamine deficiency (28). The other assessment method is a functional marker of thiamine status, transketolase activity coefficient. ThDP is a cofactor with transketolase in the pentose phosphate pathway; *in vitro* measurement of the activity of transketolase before and after the addition of excess ThDP reveals the original level of ThDP saturation, indicating thiamine adequacy (1,25). An erythrocyte transketolase activity coefficient >1.25 is commonly used as a cut-off for thiamine deficiency (1).

3.4 Efforts to improve perinatal thiamine intake

Low maternal thiamine intake reduces the thiamine concentration of human milk (18). Infantile thiamine deficiency and beriberi are not normally seen in countries where maternal thiamine intake is adequate (29). Both supplementation and fortification interventions have been employed in an attempt to improve maternal thiamine status as a means of preventing infantile thiamine deficiency. Between 1987 and 1990 there was an outbreak of infantile beriberi in the Mae La refugee camp on the Thai-Burmese border that accounted for 40% of infant mortality (15,16). As a preventative measure, lactating women in this camp were provided with a weekly 10 mg thiamine supplement until 9 months postpartum (15). However, supplementation has several challenges, including high cost, issues of distribution and a sustainability, and compliance.

3.5 Thiamine fortification

Fortification is a potentially more suitable alternative to supplementation, as it is a sustainable, cost-effective, and passive intervention (30–33). Fortification is a highly successful public health intervention; for example, two thirds of the world's population has access to iodized salt (34), and folic acid fortification in Canada and elsewhere has reduced the incidence of neural tube defects (35). Wheat flour is fortified in many countries (36), however this is not appropriate in Cambodia and other countries where wheat flour is not a food staple. We recently conducted a randomized controlled efficacy trial of thiamine-fortified fish sauce, and found that consumption over 6 months improved blood and human milk thiamine concentrations of mothers, their breastfed infants < 6 months, and children < 5 years (10,11). However, centrally produced fish sauce may not reach the poorest communities who make their own fish sauce, and fish sauce consumption is not universal in all regions where we find thiamine deficiency (37,38).

3.6 Salt as a fortification vehicle

Salt is a common condiment in most regions of the world, and has proven to be a successful global fortification vehicle for iodine (39). Current estimates suggest usual per capita salt intake in Cambodia is 15 g/day (40). However, we do not know how much is consumed at the individual level. In addition, the WHO has been actively promoting salt reduction programs globally with a goal to decrease salt intake to 5 g/day (41), therefore new measures of salt intake are required.

3.7 Summary of rationale

Suboptimal maternal thiamine intake puts exclusively breastfed infants at risk of low thiamine status, impaired cognitive development, and infantile beriberi, which can be fatal. Thiamine fortification of salt is a potentially low-cost and sustainable means of combating suboptimal thiamine status, however knowledge gaps must be filled before thiamine fortification can proceed. There is limited data available on the dose of thiamine required by lactating women to optimize the thiamine concentrations in their milk. Further, usual salt intake among lactating women is unknown. Finally, although there is emerging evidence that low thiamine intake in early life impacts cognitive development, this has yet to be assessed in a controlled research environment. The overall aim of this study is to obtain the information necessary to formulate a thiamine-fortified salt for future use in Cambodia (ideal dose, usual salt intake), and to explore the impact of various doses of maternal thiamine on markers of infant cognitive development.

4. Study Objectives

Primary Outcome and Analysis Objective:

To estimate the dose on the dose response curve where additional maternal intake of thiamine (oral dose) no longer meaningfully increases human milk total thiamine concentration at 24 weeks postpartum.

Secondary Outcomes and Analysis Objectives:

1. To estimate the dose on the dose response curve where additional maternal intake of thiamine (oral dose) no longer meaningfully increases infant thiamine diphosphate concentrations (ThDP) 24 weeks postnatally, and assess whether this depends on the presence/absence of a genetic hemoglobin disorder.
2. To estimate the dose on the dose response curve where additional maternal intake of thiamine (oral dose) no longer meaningfully increases human milk total thiamine concentration at 4 and 12 weeks postpartum.
3. To estimate the dose on the dose response curve where additional maternal intake of thiamine (oral dose) no longer meaningfully increases infant transketolase activity at 24 weeks postnatally, and assess whether this depends on the presence/absence of a genetic hemoglobin disorder.
4. To estimate the dose on the dose response curve where additional maternal intake of thiamine (oral dose) no longer meaningfully increases maternal ThDP at 24 weeks postpartum, and assess whether this depends on the presence/absence of a genetic hemoglobin disorder.
5. To estimate the dose on the dose response curve where additional maternal intake of thiamine (oral dose) no longer meaningfully increases maternal ETKac at 24 weeks postpartum, and assess whether this depends on the presence/absence of a genetic hemoglobin disorder.
6. To test for differences between the 4 randomised groups on human milk total thiamine at 4, 12, and 24 weeks postpartum.
7. To test for differences between the 4 randomised groups on maternal ThDP at 24 weeks postpartum, and assess whether this depends on the presence/absence of genetic hemoglobin disorder.
8. To test for differences between the 4 randomised groups on maternal ETKac at 24 weeks postpartum and assess whether this depends on the presence/absence of a genetic hemoglobin disorder.
9. To estimate usual household salt intake from mean fortnightly salt disappearance (weight lost, in g).
10. To estimate salt intake among a subset of 100 lactating women, their male partners (if applicable), and their children 24-59 months (if applicable) using observed weighed salt intake records.
11. To estimate sodium intake using 24 hr urinary sodium concentrations among a subset of 100 lactating women.
12. To test for differences between the 0 & 10 mg randomised groups on Composite Mullen and the 5 subscales of the Mullen at 24 and 52 weeks postnatally.
13. To test for differences between the 0 & 10 mg randomised groups on Visual Paired Comparison Novelty Score and the attention and processing speed subscales at 24 and 52 weeks postnatally.

14. To test for differences between the 0 & 10 mg randomised groups on the Language Preference Task Score at 24 and 52 weeks postnatally.
15. To test for differences between 0 & 10 mg randomised groups on oculomotor scores at 24 and 52 weeks postnatally.
16. To determine the effect of inflammation, as measured by C-reactive protein (CRP) and α -1-acid-glycoprotein (AGP) on maternal ThDP at 2 and 24 weeks postpartum, and infant ThDP at 24 weeks postnatal.

5. Study Design

This will be a double-blind, four-parallel arm randomized controlled trial, in which 320 women and their newborn infants will be enrolled. Each dyad will participate in the study between 2 and 24 weeks postnatal, a 22-week intervention period. The primary outcome measure is human milk thiamine concentrations at 24 weeks postpartum (see **Figure 1**). There are additional cognitive assessments at 12 months (52 weeks) postnatal.

[figure not shown]

Figure 1: A pictorial description of the study design and data collection scheme.

6. Study Treatments

6.1 Description of study arms

The four study arms are described in **Table 1**, below.

Table 1: Treatment arms for the trial.

Treatment Arm	Rationale	Thiamine Dose
Negative Control	Negative Control (placebo)	0 mg/d
EAR	1 x thiamine EAR for lactating women (1)	1.2 mg/d
Double EAR	2 x thiamine EAR for lactating women (1)	2.4 mg/d
Positive Control	Positive Control (dose currently given in supplemental form in Myanmar)	10 mg/d

Supplements will be opaque capsules containing varying amounts of thiamine hydrochloride and cellulose filler, as indicated in **Table 1**. All thiamine is delivered as thiamine hydrochloride, calculated using a 1.271 correction factor (ratio of molecular weights of thiamine hydrochloride and

thiamine). Capsules will be formulated and compounded by pharmacist [name] at the Quinpool Wellness Centre in Halifax, Nova Scotia, Canada.

6.2 Treatment arm codes and packaging of study capsules

Statisticians at the South Australian Health and Medical Research Institute (SAHMRI) will create a total of 8 alpha-numeric codes consisting of 3 letters followed by 8 numbers to label study supplements, two sets of codes per treatment arm.

Study capsules will be packaged in 14-capsule blister packs and delivered to the participants every two weeks. These blister packs will contain the following labeling in both English and Khmer:

- “For research purposes only”
- “Could contain up to 10 mg thiamine (vitamin B1)”
- “Take one capsule each morning”
- best before date
- alpha-numeric treatment code
- days of the week on each blister slot
- study ID and barcode (individualized sticker)

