6.4 Compliance

Compliance will be assessed fortnightly: field staff will visit the participant's home to pick up the old blister pack and complete a capsule count, and to deliver a new blister pack. A woman will be considered compliant if she consumes $\geq 80\%$ capsules over the 22-week intervention.

In an attempt to ensure high compliance, participants will interact with the same field staff person throughout the entire study in hopes of building rapport. This field staff person will complete in-person check-ins fortnightly throughout the study, and will also make weekly phone calls to encourage women to continue consuming their study capsules daily. All participants will be provided with a mobile phone as part of this study.

We are also conducting a small compliance pilot study in advance of this randomized controlled trial to determine if additional reminders in the form of daily voice messages (e.g. [Verboice](#)) or text SMS, in addition to the weekly phone calls and fortnightly visits, are warranted.

7. Sample Size

To detect a clinically meaningful difference of 40 $\mu\text{g}/\text{L}$ in human milk total thiamine concentration between any two treatment groups with 90% power, assuming a SD of 43 $\mu\text{g}/\text{L}$ (estimated SD of control group in a Cambodian thiamine-fortified fish sauce trial (9)), 48 women are required per treatment group, or a total of 192 women. This sample size allows for 20% attrition and uses a two-sided alpha of 0.0083 for each of the 6 pairwise comparisons between the four treatment groups in order to control the familywise error rate at the 0.05 level using a Bonferroni adjustment for multiple comparisons. Recruitment of 320 participants (80 per group) was planned to allow for some uncertainty in the assumed values, particularly the SD which may be larger than anticipated.

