8.2 Eligibility criteria

All women must provide written informed consent to participate. Participants must meet the following criteria:

- mothers of a newborn
- aged 18-45 years
- most recent pregnancy was normal (i.e. no known chronic conditions, preeclampsia, gestational diabetes etc.), and the singleton infant was born without complications (e.g. low birth weight (<2.5 kg), tongue tie, cleft palate)
- intends to exclusively breastfeed for six months
- resides in Kampong Thom province, Cambodia, and is not planning to move in the next six months
- is not currently taking, and hasn't taken any thiamine-containing supplements over the previous 4 months
- is not currently participating in any nutrition programs beyond normal care
- is willing to consume one capsule daily from 2 weeks through 24 weeks postpartum
- is willing for her entire household consume only salt provided by the study team
- is willing for the following biological samples to be collected: a maternal venous blood sample and human milk sample at 2 weeks postpartum, a human milk sample at 4 and 12 weeks postpartum, and maternal and infant blood samples and a human milk sample at 24 weeks postpartum

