9.2 Fortnightly monitoring

Every two weeks between 2-24 weeks, a member of the research team will visit the participant in her home to distribute new blister packs and collect used blister packs (compliance measure). At this time the field staff will also ask a small number of questions about capsule compliance, selling or sharing of salt, and about infant and young child feeding (IYCF) practices (was the infant exclusively breastfed over the previous two weeks). The field staff will weigh the household salt container to assess salt disappearance, and will provide more salt to the household.

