9.7 Human milk samples

Human milk samples will be collected using a battery-powered single breast pump (Swing Breast pump, Medela) at 2, 4, 12, and 24 weeks postnatal. One full breast expression (single breast) will be collected from the breast women self-identify as being more 'full' (the breast not most recently emptied). Since time of day has little effect on milk thiamin concentrations (46), samples can be collected at any time of day, however, time of day, time since last meal, and breast side will be recorded.

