12.5 Protocol deviations

Protocol deviations will be documented and reported to the Principal Investigator if data collection does not fall within the following windows:

- chart review: anytime between 0 – 16 days postnatal
- 2 weeks postnatal: 2 weeks postnatal \pm 2 days
- 4 weeks postnatal: 4 weeks postnatal \pm 2 days
- 12 weeks postnatal: 12 weeks postnatal \pm 4 days
- 24 weeks postnatal: 24 weeks postnatal \pm 4 days
- 52 weeks postnatal: 52 weeks postnatal \pm 7 days
- fortnightly monitoring: \pm 2 days

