1 PREFACE

This statistical analysis plan (SAP) describes the planned analyses for the trial:

Trial of thiamine supplementation in Cambodia.

The following documents were reviewed in preparation of this SAP:

- Trial of thiamine supplementation in Cambodia: Protocol version 2.1 (dated 24 July 2018)
- Questionnaires and consent forms (dated 6 April 2018 and 19 July 2018)

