6.3 Measurement of treatment compliance

Treatment compliance will be assessed descriptively by treatment group based on the number of unused capsules (Module 1.2 from Fortnightly monitoring data collection sheet) counted every fortnight over the 22 week intervention period.

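### Capsule supply has no slack: visits that are on protocol can leave a willing woman without capsules, including before a late 24-week milk sample

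*Combined protocol and SAP*

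**What the plan says.** **Supply.** Protocol 6.2: "Study capsules will be packaged in 14-capsule blister packs and delivered to the participants every two weeks". SAP 3.3 repeats this and sets one capsule a day. Section 9.2 gives the visits: "Every two weeks between 2-24 weeks, a member of the research team will visit the participant in her home to distribute new blister packs". In 6.4 the staff member comes to "pick up the old blister pack and complete a capsule count, and to deliver a new blister pack". Neither document describes a reserve for participants. The packs kept at village chiefs' homes (Product accountability) are for testing capsule content.

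**Dosing period.** Protocol 8.2 requires that a woman "is willing to consume one capsule daily from 2 weeks through 24 weeks postpartum", and SAP 3.3 gives the same period. Neither says what she should do if the 24-week sample is late.

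**Timing.** Protocol 12.5 asks for a deviation to be documented "if data collection does not fall within the following windows": ±2 days for fortnightly monitoring and ±4 days for the 24-week collection. It does not say whether the fortnightly window is counted from the scheduled date or from the previous visit.

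**What is recorded.** With the milk sample, "time of day, time since last meal, and breast side will be recorded" (9.7). SAP 6.3 describes compliance "based on the number of unused capsules (Module 1.2 from Fortnightly monitoring data collection sheet) counted every fortnight". Section 9.2 also has staff ask a few questions about capsule compliance at each visit. The field forms are not available here, so they may already hold a last-capsule date.

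**The concern.** The supply matches the calendar only if visits are exactly 14 days apart, but the visit windows allow longer intervals. The primary outcome is a single milk concentration at 24 weeks, related to assigned dose through the Emax curve. That collection also has a wider window than the fortnightly visits that bring the capsules, and the documents do not say that dosing continues until a late sample is taken.

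A woman who takes every capsule she is given could thus be sampled some days after her last one. In the placebo arm this changes nothing. In the 1.2, 2.4 and 10 mg arms the likely direction is lower milk thiamine, so the effect would not cancel across arms. The capsule count does not reveal such a lapse, because an empty pack looks the same whether the last capsule was taken yesterday or four days ago.

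**Working it through.** Inputs: 14 capsules per pack and one capsule a day (protocol 6.2, SAP 3.3); a 22-week intervention (protocol 1.5); windows of ±2 and ±4 days (12.5). Convention: a pack covers 14 days from the day of hand-over. If the visit-day capsule comes from the old pack, counts can shift by one day.

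1. **Planned supply.** 22 × 7 = 154 days. Hand-overs at weeks 2, 4, …, 22 make 11 packs, and 11 × 14 = 154 capsules. The surplus is 0.

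2. **Ordinary interval.**
   - Window counted from scheduled dates, leftovers collected: one visit 2 days early and the next 2 days late gives 14 + 2 + 2 = 18 days, and 18 − 14 = 4 days without capsules.
   - Window counted from the previous visit: 14 + 2 = 16 days, so 2 days without.
   - The early visit follows an on-time one and she keeps the 2 capsules left over: 18 − 16 = 2 days without.

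3. **Before the 24-week sample, with no further pack first.** The week-22 visit is on day 154 + a (a = −2 to 2) and the sample on day 168 + b (b = −4 to 4). Gap = max(0, b − a).
   - Week-22 visit on time, sample 4 days late: 4 − 0 = 4 days. This depends neither on where the window is anchored nor on what happens to leftovers.
   - Week-22 visit 2 days early, sample 4 days late: 4 + 2 = 6 days, which is 1 of 45 pairs.
   - All 45 pairs: 0 days in 25, 1 in 5, 2 in 5, 3 in 4, 4 in 3, 5 in 2, 6 in 1. So 20 of 45 leave a gap.
   - A pack handed over on day 152 lasts through day 165. Only days 166 and 167 can be uncovered before day 168, so at most 2. The rest fall after the stated end of dosing.

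4. **With a week-24 pack.**
   - Delivered with the sample, both within ±2 days: 10 of 25 pairs leave a gap, at most 4 days (1 pair).
   - Delivered separately on day 168 + c (c = −2 to 2), sample within ±4 days: uncovered days = max(0, min(b, c) − a). That is above 0 in 50 of 225 combinations. In 30 of the 50 the new pack arrives before the sample. In 20 the gap runs up to the sample, reaching 4 days in one.

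5. **Whole course, worst on-protocol pattern, leftovers collected.** Visits alternate late and early, and the 24-week visit is 4 days early: five 18-day intervals give 5 × 14 = 70, five 10-day intervals give 50, and a last 8-day interval gives 8. The total is 128, and 128/154 = 83%. With ±2 days at the last visit: 6 × 10 + 5 × 14 = 130, and 130/154 = 84%.

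6. **What the count shows.** In an 18-day interval she uses 14 of 14 capsules (100%) but is covered on 14 of 18 days (78%).

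**The case against.** Section 12.5 sets a threshold for reporting data collection that is off schedule; it is not a delivery schedule. The plan is a visit every two weeks, by the same staff member, with weekly phone calls. Evenly spaced visits, including consistently early or late ones, leave no gap if the sample keeps the same spacing. This stands to the extent that none of the counts above can be read as a frequency. But packs are exchanged at the fortnightly visits, so their ±2 days governs supply as well as data.

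Two further points stand. The 4-day figure for an ordinary interval rests on an unstated anchor and on leftovers being taken away. And most of the days that can be lost before a late sample come after the stated end of dosing, so they are not a shortfall of promised supply. For the primary measurement the result is nevertheless the same: milk taken after the capsules ran out.

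The capsule count is not the only safeguard. Staff ask about compliance at each visit, and days without supply can be derived from visit dates. That makes better recording useful but not essential.

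A reader might infer from the 78% that supply gaps would push women out of the per-protocol set. They would not: that set is defined over 22 weeks at 80% of capsules, and the worst pattern gives 83%.

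A reader might also infer that the Emax estimate is biased by a material amount. The documents give no rate at which milk thiamine falls after stopping. As a pure assumption, if the supplement-related rise halved every t days, a 4-day gap would remove 1 − 0.5^(4/t) of it: 94%, 60%, 33% or 18% for t = 1, 3, 7 or 14. That range is too wide to support any statement about the 90% dose.

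**Conclusion.** The point holds as a minor one: a cheap improvement, not an error in the plan. On-protocol timing can leave a willing woman without capsules, for up to 2 days in an ordinary interval, or up to 4 under the stricter reading. Before a late primary sample the gap can be up to 4 days, and 6 only if the week-22 pack is the last before the sample, comes 2 days early, and the sample is 4 days late. A week-24 pack that arrives before the sample ends the gap.

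This rests on three assumptions: that no reserve is described because none is given, that a pack lasts 14 days from hand-over, and that the windows in 12.5 are used in practice. How often gaps would occur, and what they would do to milk thiamine or to the estimated dose, cannot be derived from the documents. Only the active arms could be affected.

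**What to change.** In protocol 6.2 and 6.4, give each woman a reserve of about 6 capsules of her own treatment code. Replace it if used and include it in the capsule count. Six covers the longest permitted stretch before the primary sample (20 − 14 = 6). State that she takes one capsule daily until the 24-week milk sample is collected, and align the dosing period in protocol 8.2 and SAP 3.3.

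Optional: record the date of the last capsule at that sample, unless the field form already does, and describe days without supply from visit dates next to the capsule count in SAP 6.3.

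An analysis that excludes women with a gap is best left out, or labelled exploratory, because it selects on an event after randomisation.

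Cost: 6 × 320 = 1,920 capsules, against 11 × 14 × 320 = 49,280 planned, or 3.9%. If a week-24 pack is also supplied, the base is 12 × 14 × 320 = 53,760 and the share 3.6%. Replacements for used reserves come on top. The downside is slightly more capsules and capsule accounting; no extra staff or procedure is needed.
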